5 INTERIM ANALYSES

No formal interim analysis is planned for the study.

The first set of analyses will be run after the primary DBL, which will occur after all randomized participants have completed the initial 16-week treatment period or discontinued prior to Week 16. The final set of analyses will be produced at the final DBL, which will occur when all participants have completed the 52-week treatment period and/or the IPD/EOT/Week 60 follow-up visit.

An additional analysis may be performed between the primary and final DBLs to report data accumulating during the extension part of the study if needed to support end of Phase 2 decision making.

Participants and investigators will remain blinded to the dosing regimens until the final DBL.

6 CHANGES OF ANALYSIS FROM PROTOCOL

Section 2.2.5 Extension period analysis set is added to identify all participants who enter the extension period.

Sections 3.5.11 and 4.2.9.11 Biomarker analyses added to present in SAP and CSR.

8 APPENDIX

8.1 Accounting for missing data

Missing data can occur due to intercurrent events like non-adherence to randomized treatment, or early discontinuation, or non-adherence of ePRO usage. The amount of missing data is

minimized in this study as participants are encouraged to remain in the study after premature discontinuation of IP and complete visits according to the protocol.

This section summarizes how we will describe the pattern of and reasons for missing data from the study. It will also describe how we plan to account for missing data, including both the primary and sensitivity analyses to assess the robustness of the treatment effect under different underlying assumptions to account for missing data.

8.1.1 Missing data description

Tabular summaries for the percentage of participants by the reason for discontinuation of randomized treatment as well as for withdrawal from the study will be presented by treatment to describe why participants discontinue from randomized treatment or withdraw from the study. The time to discontinuation of randomized treatment and withdrawal from the study will be presented using Kaplan Meier plots (overall and split by treatment related/not treatment related reason for discontinuation, as defined in [Table 12](#)). Dependent on these outputs additional exploratory analyses may be produced as deemed necessary to further understand the pattern of missing data.

Descriptive summaries of number and percentage of participants using rescue medication and change of background medications will be provided by treatment group.

For primary endpoint and key secondary endpoints, the summaries of number and percentage of participants with missing/non-missing daily assessments will be presented by treatment group and visit.

8.1.2 Multiple imputation (MI) approach

Analyses will include all participants in the FAS.

The following 4 steps will be used to build the imputation datasets and perform analyses:

- 1 100 datasets with a monotone missing pattern will be obtained, induced by Markov Chain Monte Carlo (MCMC) method up to Week 16, on participants with missing data not due to reason of interest (eg lost-to-follow-up).
- 2 For each of the imputed datasets obtained in step 1, the remaining missing data due to reason of interest (eg AE) up to Week 16, will be imputed using the regression method for the monotone pattern with adjustment for covariates as for the primary model.
- 3 Each of the 100 imputed datasets will be merged with the one dataset imputed by worst case carried forward (WOCF) approach, and then be analyzed using the main statistical model. These 100 datasets will be saved.
- 4 Apply Rubin's rule ([Rubin DB 1987](#)) to combine analysis results (point estimates and standard errors) from 100 imputations. Descriptive statistics including number of

participants, mean, standard error, and least squares (LS) means will be provided for each timepoint. In addition, difference in LS means and the corresponding 95% CIs will be provided along with the p-values for Week 16.

8.1.3 Primary analysis for continuous endpoints under effective estimand using the Missing at Random (MAR) assumption

The primary analysis for the continuous endpoints allows for differences in outcomes over the study treatment period up to 16 weeks. This analysis includes all data until participants withdraw from the study or up to Week 16, whichever is earlier, regardless of if they discontinue from randomized treatment. Data after rescue therapy taken after Day 29 will be considered as missing. The primary analysis uses a MMRM method, adjusting for covariates (Section 4.2.7.3), and assumes that missing data is missing at random (MAR) and is a direct likelihood approach (DL).

8.1.4 Sensitivity analyses: Primary estimand assuming dropout reason-based multiple imputation approach

To examine the sensitivity of the results of the primary analysis to departures from the underlying assumptions, additional analyses will be performed. As with the primary analysis the sensitivity analyses include all data until participants withdraw (up to Week 16) from the study regardless of if they discontinue from randomized treatment.

For sensitivity analyses, missing data will be imputed using controlled sequential MI methods based on pattern mixture models (EMA/CHMP/EWP 2010). This model will assume that some pre-specified subset of participants who withdraw from the study have correlations with future unobserved visits similar to participants in the placebo arm.

The default assumptions that will be used to impute the missing data are as follows:

- (a) MAR: Assumes that the trajectory for participants who dropped out in each arm is similar to those observed in their own treatment arm.
- (b) Dropout Reason-based Multiple Imputation (DRMI): Assumes that the trajectory for participants in the benralizumab arms who dropped out for a treatment related reason or severe non-compliance of protocol is similar to that of the placebo participants, whereas the remaining participants who dropped out are imputed assuming MAR.

A summary of reasons for participants withdrawing from the benralizumab treatment arm and the corresponding treatment arm used to calculate the imputation response rate under MAR and DRMI is given in Table 12.

Table 12 Parameters for calculating the imputation under MAR and DRMI

Reason for withdrawal	MAR	DRMI
Adverse Event	Benralizumab	Placebo

Reason for withdrawal	MAR	DRMI
Development of study-specific discontinuation criteria*	Benralizumab	Placebo
Death	Benralizumab	Placebo
Severe non-compliance to protocol	Benralizumab	Placebo
Eligibility criteria not fulfilled	Benralizumab	Benralizumab
Participant lost to follow up	Benralizumab	Benralizumab
Participant decision	Benralizumab	Based on review prior to study unblinding
COVID-19	Benralizumab	Benralizumab
Other	Benralizumab	Based on review prior to study unblinding

Note: Participants in the placebo arm are imputed using the mean of the non-missing values in placebo arm.

* Development of study-specific discontinuation criteria are based on the following: Anaphylactic reaction to the investigational product requiring administration of epinephrine; Development of helminth parasitic infestations requiring hospitalization; If 2 doses of the IP are missed during course of the study; A respiratory-related event requiring mechanical ventilation.

Some reasons for withdrawal are clearer to determine as treatment related (AEs, Death, Development of study-specific discontinuation criteria) or non-treatment related (participants lost to follow up, eligibility criteria not fulfilled). Other reasons are less clear such as participant decision and ‘Other’; a review of each participant who withdraws from the study will therefore be carried out prior to unblinding the study. The review will include assessment of the reason for discontinuation of randomized treatment for those participants who discontinued randomized treatment and then withdrew from the study and also free text for when the reason for withdrawal or discontinuation of randomized treatment is recorded as subject decision or other. Based on this review the default assumptions for DRMI as described in b) and [Table 12](#) may be changed. A list of these participants and the assumptions made under DRMI will be documented prior to unblinding of the study.

Together with the primary analysis, the sensitivity analyses are considered to cover the range from realistic to plausible worst-case assumptions about missing data.

The DRMI approach has been selected as a conservative approach based on the fact that placebo participants are receiving standard of care and are not expected to change to a substantially more effective treatment after withdrawing from study or study treatment. For participants receiving benralizumab who withdraw from the study due to treatment related reasons it is assumed that at worst they would be on the standard of care treatment, i.e., the placebo treatment group. For participants receiving benralizumab who withdraw from the study due to non-treatment related reasons it seems reasonable to assume they would be similar to those participants who complete treatment.

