[Figure 1](#) presents an overview of investigational product (IP) administration for each randomized treatment group.

Figure 1 Investigational Product Administration Q4W by Randomized Treatment Sequence

^a In the extension phase, participants will receive benralizumab on a Q8W or Q4W dosing regimen, as predetermined at randomization (Visit 2). Participants randomized to receive benralizumab Q8W in the extension phase will also receive placebo at intervening study visits when they are not receiving benralizumab.

Q4W, every 4 weeks; Q8W, every 8 weeks.

All participants who prematurely discontinue IP (IPD) should return to the study site for the IPD visit 4 weeks (± 7 days) after the last dose of IP for procedures, or as soon as feasible if this interval is missed (eg, if decision on discontinuation was made later), as specified in Table 3 of the CSP.

[figure not shown]
At the IPD visit, the participant will be offered the following options for further follow-up:

- Participants are encouraged to return to all scheduled site visits and perform all procedures but without IP administration, until the end of the study (Visit 16).
- Participants unwilling or unable to attend the scheduled site visits until the end of the double-blind treatment period, will be offered a follow-up option that includes monthly telephone contact instead. During follow-up telephone contact, the Investigator will collect information about concomitant medications, information on AD symptoms, and AE/SAE(s).

All Week 16 analyses at primary database lock (DBL) will evaluate the two initial dose treatment arms: benralizumab 30 mg (total $n = 80$), and placebo (total $n = 80$). Analyses of data for Week 52 end of study reporting will include data from the entire study, presenting the three randomized treatment groups: benralizumab followed by Q4W, benralizumab followed by Q8W and placebo followed by benralizumab Q4W-Q8W.

For an overview of the study design, see [Figure 2](#). For further details see CSP Section 4.1.

Figure 2 Study Design

^a To maintain blinding, participants will receive investigational product every Q4W during the extension period. Placebo will be administered Q8W, occurring 4 weeks after each benralizumab administration. n, number; Q4W, every 4 weeks; Q8W, every 8 weeks.

Participants and Investigators will remain blinded to the treatment and regimen until the final DBL.

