3.3.2 Peak Pruritus Numeric Rating Scale

The proportion of participants with an improvement of ≥ 4 points in peak pruritus weekly score at Week 16 will be used as the second key secondary efficacy variable.

The Peak Pruritus NRS is a one-item daily assessment of the worst itch the participant experienced over the past 24 hours. This is recorded every evening from Visit 1 onwards on the electronic device supplied to the participants. The score ranges from 0 to 10, with 0 being “no itch” and 10 being “worst itch imaginable.” and so a reduction in score is considered an improvement.

If a participant has at least 4 non-missing daily scores in a 7-day week, the peak pruritus weekly score is defined as the sum of the available daily scores divided by the number of days with non-missing daily scores. If there are less than 4 non-missing daily scores, then the weekly score is missing for that week.

The second key secondary endpoint is a binary response that will classify a participant as a responder if there is an improvement of 4 or more points in peak pruritus weekly score at Week 16 relative to baseline. Otherwise, participants will be classified as a non-responder.

In the statistical analyses, a binary variable will take on value 1 if a participant is defined as a responder, and value 0 for non-responder, and will be used as the response variable for the efficacy analysis.

The change from baseline in peak pruritus score at Week 2 will be analyzed as a secondary endpoint.

Intercurrent events will be considered as described above in Section Intercurrent Events (Section 3.1.5). Participants with a missing baseline score will have missing change from baseline status. Intercurrent events will be considered for analyses and descriptive summaries.

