3.3.3 Patient-Oriented Eczema Measure (POEM)

The change from baseline in Patient-Oriented Eczema Measure (POEM) score at Week 16 will be analyzed as a secondary endpoint.

The POEM is a continuous outcome that will be completed at the on-site visits specified in the SoA (CSP Table 3) on an electronic device supplied to the site.

The POEM is a 7-item assessment of AD symptoms (itchiness, sleep disturbance, bleeding, weeping, cracking, flaking, and dryness) that characterizes severity as a function of symptom frequency. The participant responds to each of the 7 questions by selecting the approximate number of days “over the last week” when they experienced the symptom, scored as 0 (no days), 1 (1 to 2 days), 2 (3 to 4 days), 3 (5 to 6 days), or 4 (every day).

The seven items are summed, resulting in a score ranging from 0 to 28 (Table 5). Higher scores represent more severe AD symptoms.

Table 5 Patient-Oriented Eczema Measure Score Bands

Score range	Clinical interpretation
0 to 2	Clear or almost clear
3 to 7	Mild atopic dermatitis
8 to 16	Moderate atopic dermatitis
17 to 24	Severe atopic dermatitis
25 to 28	Very severe atopic dermatitis

The ePRO does not allow for questions to be unanswered, so no consideration is required for missing items.

Intercurrent events will be considered as described above in Section Intercurrent Events (Section 3.1.5). Intercurrent events will be considered for analyses and descriptive summaries.

Changes from baseline in POEM score at Week 52 will be analyzed.

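### The dropout-reason-based imputation gives a placebo reference only to study withdrawals, so benralizumab participants who stop product early and move to telephone follow-up fall by default under missing at random

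*SAP*

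**What the plan says.** SAP section 1.1.1 separates stopping investigational product (IP) from leaving the study. Everyone who stops IP should attend an IP discontinuation (IPD) visit 4 weeks (±7 days) after the last dose. At that visit they are encouraged to keep attending. Those unwilling or unable to do so until the end of the double-blind period "will be offered a follow-up option that includes monthly telephone contact instead". The calls collect concomitant medication, information on symptoms and adverse events; no scored clinic assessment is listed.

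The continuous clinic endpoints need a visit. POEM, for example, is a "continuous outcome that will be completed at the on-site visits specified in the SoA" (section 3.3.3), and SCORAD, DLQI, CDLQI and EASI are likewise tied to scheduled visits and a device held at the site. Peak Pruritus NRS is the exception: "This is recorded every evening from Visit 1 onwards on the electronic device supplied to the participants" (section 3.3.2).

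Section 8.1.4 defines DRMI. The placebo-based assumption applies to "some pre-specified subset of participants who withdraw from the study"; the remaining dropouts are imputed under missing at random (MAR). Table 12 is introduced as "A summary of reasons for participants withdrawing from the benralizumab treatment arm", and its first column is the reason for withdrawal. The blinded review covers each participant who withdraws, and it examines the reason for stopping treatment "for those participants who discontinued randomized treatment and then withdrew from the study". The section concludes that the primary and sensitivity analyses together span realistic to plausible worst-case assumptions.

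**The concern.** A benralizumab participant who stops IP for an adverse event and has no later scores is the kind of case DRMI is meant to stress. If that participant also leaves the study, Table 12 assigns a placebo reference. If the same participant accepts telephone contact, the clinic scores are just as absent, but there has been no study withdrawal, and no row, rule or review step assigns a placebo reference.

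The difference between these two people is administrative. It says nothing about how they would have scored off drug. The SAP relies on this analysis: section 8.1.5 treats reasonably similar estimates as assurance that missing data do not matter. A check that leaves out part of its target group agrees with the primary mixed model more readily than it should.

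**Working it through.** **1. Is the group distinct from withdrawals?** Yes, on the SAP's own terms. Section 4.2.1 counts participants off IP but still in follow-up separately from those who withdraw. Table 3 in section 3.1.5 separates missing data in a participant who remains in the study from the withdrawal categories.

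**2. Who in the group lacks a Week 16 clinic score?** Doses in the controlled period are at Weeks 0, 4, 8 and 12 (section 1.1.2), and the IPD visit falls about 4 weeks after the last dose:
- last dose Week 12: 12 + 4 = Week 16, so a Week 16 score can exist;
- last dose Week 8: 8 + 4 = Week 12, so the Week 16 score is missing under telephone follow-up;
- last dose Week 4 or Week 0: scores end at about Week 8 or Week 4.

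If the visit timing is kept, the gap concerns those who stop before the Week 12 dose.

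**3. Rule against rationale.**
- Keyed to study withdrawal: the model statement, Table 12 and the blinded review, all in section 8.1.4.
- Wider than withdrawal: the justification in section 8.1.4, which speaks of leaving either the study or the study treatment; the Kaplan-Meier plots in section 8.1.1, which apply the Table 12 split to treatment discontinuation too; and the Table 12 footnote, which includes an IP criterion (two missed doses).

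**4. Size.** The SAP states no figure for this rule and gives no withdrawal rate, telephone rate or SD. All rates below are assumptions. Let D be the treatment difference under MAR, w the share of the benralizumab arm withdrawn for a Table 12 placebo reason, and t the share who stopped IP for such a reason, chose telephone contact and have no Week 16 score. Treat imputed outcomes as fully placebo-like, with no information from the participant's own earlier scores.
- DRMI as written: D × (1 − w)
- DRMI extended to the telephone group: D × (1 − w − t)
- Omitted shift: t × D
- Fraction of the intended shift omitted: t / (w + t)

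| w | t | t × 80 participants | As written | Extended | t/(w+t) |
|---|---|---|---|---|---|
| 3% | 2% | 1.6 | 0.97 D | 0.95 D | 40% |
| 3% | 5% | 4 | 0.97 D | 0.92 D | 62.5% |
| 3% | 10% | 8 | 0.97 D | 0.87 D | 77% |
| 5% | 2% | 1.6 | 0.95 D | 0.93 D | 29% |
| 5% | 5% | 4 | 0.95 D | 0.90 D | 50% |
| 5% | 10% | 8 | 0.95 D | 0.85 D | 67% |

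The omitted shift is therefore 2% to 10% of D. With an assumed D of 6 EASI points it is 0.02 × 6 = 0.12 to 0.10 × 6 = 0.6 points.

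**The case against.** **The MAR assignment is an inference.** A reader might take the SAP to say outright that these participants are imputed from the benralizumab arm. It does not. No sentence names them, the term *dropped out* in the DRMI definition is undefined, and step 2 of the algorithm in section 8.1.2 refers to missing data due to a reason of interest, with an adverse event as its example. A programmer could read that to include an adverse-event-driven IP stop. This stands as a limit on the point. It does not remove it: the model statement, the table and the review all point to withdrawal, and two programmers could classify the same participant differently.

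**The group is smaller than it looks.** The IPD visit can supply the Week 16 score after a Week 12 dose, and Peak Pruritus NRS may continue at home. Both stand, so it would be wrong to say that telephone follow-up means no scores at all.

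**MAR does not mean full benefit.** A reader might infer that these participants are assumed to keep the whole benralizumab effect. MAR imputation conditions on their own observed scores, including any IPD score, and the benralizumab arm contains off-drug data from those who stopped but kept attending. The sizes above are therefore upper bounds.

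**The stakes are limited.** The continuous endpoints lie outside the testing hierarchy, and section 4.2.7.3 makes multiple imputation conditional on the amount of missing data, although section 8.1.4 is worded more firmly. This also stands and sets the priority.

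**The protocol is not shown.** It may define withdrawal or telephone status more closely. The imputation rule itself, however, is set out in the SAP.

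**Conclusion.** The point holds as a gap in one sensitivity analysis. As worded, DRMI gives a placebo reference only to study withdrawals. Benralizumab participants who stop IP before the Week 12 dose for a Table 12 placebo reason and choose telephone follow-up receive none, and by default fall under MAR. This affects change from baseline at Week 16 in EASI, SCORAD, POEM, DLQI and CDLQI. The omitted shift is at most about t × D, or 2% to 10% of the effect for an assumed t of 2% to 10%; the SAP supplies no rate to narrow that range.

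A reader might infer that the primary result is at risk. The document does not support this: for the primary and key secondary binary endpoints these participants are non-responders because their data are missing (sections 3.1.5 and 4.2.6.1). That would change only if imputation were adapted to binary endpoints, which section 4.2.6.3 leaves open. Nor has any conclusion on a continuous endpoint been shown to change. The priority is low, but the stated range of assumptions is narrower than the SAP claims.

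**What to change.** In section 8.1.4 and Table 12, apply the DRMI reference by reason for IP discontinuation or for study withdrawal to any participant who stopped IP and has later missing scores, whether withdrawn or in telephone follow-up. Scores actually observed after stopping IP stay in the analysis as recorded. Define *dropped out* to match, and align the reason-of-interest wording in section 8.1.2. Extend the blinded review to these participants, and document before unblinding which reason governs when the reason for stopping IP and the reason for withdrawal differ.

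The cost is SAP wording and a few more cases to review. Section 8.1.1 already tabulates the reasons for stopping treatment, so no new data are needed. The downside is a slightly less favourable sensitivity estimate.

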4.2.7.3 Change from baseline in EASI score

The secondary endpoint of change from baseline in EASI score will be analyzed by a MMRM model at Week 16.

The model will include change from baseline in EASI score as the dependent variable (derived for each participant and every scheduled visit up to Week 16); baseline EASI score as a continuous covariate; treatment, age at screening (≥ 12 to < 18 years/ ≥ 18 years), blood eosinophils at screening (< 300 cells/ μ L; ≥ 300 cells/ μ L), and visit as categorical factors; and treatment-by-visit as an interaction term. The strata variables will be used as recorded on the database. An unstructured variance-covariance matrix will be used to model within-subject errors, and the Kenward-Roger approximation will be used to estimate denominator degrees of freedom and to adjust standard errors, the OBSMARGINS option will be used to derive the LSMEAN estimates assuming mean values for the baseline covariates. If the model fails to converge, alternative variance-covariance models will be tried in the following order: Toeplitz, first-order regressive, compound symmetry.

For each visit, the model will be used to estimate the mean change from baseline for each treatment group (benralizumab 30mg Q4W and placebo) and difference between treatment groups, with corresponding 95% CIs and the p-value, corresponding to a 2-sided test.

The distributional assumptions of the MMRM model will be checked by examining plots of residuals. If the residuals suggest that it is unreasonable to assume that data follow a Normal distribution (eg, data are skewed and the constant variance assumption is not met), alternative models will be explored. For example, data may be log transformed prior to fitting the model, or a non-parametric method may be deemed more appropriate.

The observed means and mean changes from baseline will be summarized using descriptive statistics by treatment group and each scheduled visit up to Week 16.

Additional sensitivity analyses based on different missing data mechanism assumptions may be used to explore the robustness of any treatment effect, including

- Participants with rescue therapy use (from Day 29 onwards) will be imputed using LOCF approach and analyzed with analysis of covariance (ANCOVA);
- Treatment policy approach where all available data is included regardless of rescue use, and analyzed with MMRM;

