8.1.5 Overall summary of analyses to account for missing data

Forest plots will be used to show the primary analysis results along with the missing data sensitivity and alternative estimand analysis results.

It is noted that if the primary analysis is statistically significant, it is not necessarily expected that all sensitivity analyses will also give statistically significant results. If the results of the sensitivity analyses provide reasonably similar estimates of the treatment effect to the primary analysis, this will be interpreted as providing assurance that neither the lost information nor the mechanisms which cause the data to be missing have an important effect on primary analysis conclusions. Based on these outputs and the drug's mechanism of action, the plausibility of the assumptions we make about missing data in the different analyses will be considered and described in the clinical study report.

The methodology described above to explore any potential impact of missing data for the primary endpoint may be repeated for other endpoints if required due to amount or pattern of missing data.

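### The note to SAP Table 12, read literally, fills missing placebo values with one observed mean, which conflicts with the multiple imputation set out in 8.1.2 and 8.1.4 (minor; MI sensitivity analyses only)

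*SAP*

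**What the plan says.** SAP Appendix 8.1 describes how placebo participants are imputed in three places.

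- **8.1.2, the MI procedure.** It covers all FAS participants. Step 1 creates 100 datasets by MCMC. In step 2 the remaining missing data "will be imputed using the regression method for the monotone pattern with adjustment for covariates as for the primary model". Step 4 applies Rubin's rule "to combine analysis results (point estimates and standard errors) from 100 imputations". No step exempts the placebo arm.
- **8.1.4, the sensitivity method.** Here "missing data will be imputed using controlled sequential MI methods based on pattern mixture models". The MAR assumption applies to both arms: "Assumes that the trajectory for participants who dropped out in each arm is similar to those observed in their own treatment arm". DRMI uses MAR for every dropout not referred to the placebo arm.
- **8.1.4, Table 12 and its note.** The rows cover withdrawals from benralizumab only. The lead-in describes the columns as "the corresponding treatment arm used to calculate the imputation response rate under MAR and DRMI". The note then adds the placebo rule: "Participants in the placebo arm are imputed using the mean of the non-missing values in placebo arm".

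Two other places bear on the consequence. In 4.2.7.3 the modelled variable is a change: "The model will include change from baseline in EASI score as the dependent variable". In 8.1.5 the missing-data analyses are taken as reassuring "If the results of the sensitivity analyses provide reasonably similar estimates of the treatment effect to the primary analysis".

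**The concern.** A mean of observed values is a single number. Inserted literally, it ignores the participant's own earlier scores and the model covariates. It is also the same in each of the 100 datasets, so Rubin's rule receives no between-imputation variance for missing placebo values. Missing benralizumab values would still be drawn at random, so the two arms would be treated differently.

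The note is also the only sentence attached to Table 12 that says how placebo participants are imputed. Two programmers could follow the SAP and produce different results. Even the literal rule is incomplete, because the values averaged could be raw scores or changes from baseline.

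At stake is how the MI sensitivity analyses are read. SAP 8.1.5 compares their estimates with the primary analysis. A run labelled MAR could show an SE that is too small and, under some dropout patterns, an estimate that departs from the MAR-based MMRM only because of the fill rule.

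**Working it through.** The plan states no figure on this point. The conflict is settled by setting the texts side by side; the arithmetic shows only how much a literal reading would matter.

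**1. The texts.**

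| Feature | 8.1.2 and 8.1.4 | Note to Table 12, literally |
|---|---|---|
| Source of placebo information | placebo arm | placebo arm |
| Use of own earlier scores | yes (monotone regression, trajectory) | none |
| Covariates | as in the primary model | none |
| Variation over 100 datasets | random draws | none |

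The source arm agrees. The method does not.

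**2. SE when dropout is unrelated to outcome.** Inputs: n per arm (80 in SAP 1.2), outcome variance s², and missing fraction m at Week 16, the same in both arms. The SAP gives no m, so 10%, 20% and 30% are assumed. Covariates are ignored here.

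- Correct variance of an arm mean: s² / [n(1−m)].
- Apparent variance after a mean fill: the sample variance shrinks to about s²(1−m), so the result is s²(1−m)/n.
- Reported over correct SE of the difference, with only placebo filled: sqrt{[(1−m) + 1/(1−m)] / [2/(1−m)]} = sqrt{[1 + (1−m)²]/2}.

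| m | Calculation | Ratio | SE understated by |
|---|---|---|---|
| 10% | sqrt(1.81/2) | 0.951 | 4.9% |
| 20% | sqrt(1.64/2) | 0.906 | 9.4% |
| 30% | sqrt(1.49/2) | 0.863 | 13.7% |

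A simulation gives similar ratios. It used 4,000 trials per setting with no treatment effect, 80 per arm, baseline plus four visits, 100 imputations, Rubin's rules, and AR(1) 0.8 or exchangeable 0.6 correlation. Mean SE over empirical SD was 0.947-0.961, 0.893-0.919 and 0.862-0.871 across both fills, against 0.996-1.030 for regression MI in both arms. Coverage of the 95% CI was about 94%, 92-93% and 91%, against 95-96%.

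**3. Bias when dropout depends on earlier scores.** Same design in large samples, with dropout logistic in the previous visit's score and 10-30% missing. Higher scores are worse, and worse participants leave more often.

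| Assumed log-odds per SD | Raw-score fill (against benralizumab) | Mean-change fill (in its favour) |
|---|---|---|
| 0 | none | none |
| 0.25 | at most 0.05 SD | at most 0.015 SD |
| 0.5 | 0.03-0.10 SD | at most 0.03 SD |
| 1 | 0.06-0.18 SD | 0.01-0.04 SD |

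At 80 per arm and log-odds 1, the 4,000-trial simulation gave 0.060-0.174 SD (raw score) and 0.008-0.046 SD (mean change), which agrees within simulation error. Regression MI in both arms stayed within 0.0043 SD of zero. For scale, the SE of the difference is 0.13-0.18 SD.

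**4. Limits.** The simulated analysis is an ANCOVA at Week 16 in place of the main model. It leaves out the stratification factors and the MCMC and worst-case steps of 8.1.2. The figures show order of magnitude, not the departure from the SAP's exact procedure.

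**The case against.** The strongest reply is that the note is shorthand. Table 12 concerns parameters for the imputation, its cells only name a source arm, and it has no placebo row. On that view the note supplies the missing row, and the surrounding text already fixes the method as sequential MI with Rubin pooling. This is plausible, and if it is what was meant, every figure above falls away. It still leaves a sentence that names a mean of observed values rather than an arm, so the wording needs correcting either way.

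Second, the larger bias figures need a raw-score fill, whereas the modelled variable in 4.2.7.3 is change from baseline. A mean-change fill is therefore the more natural literal reading, and its bias is small against the SE. That stands. So does the point that the bias is roughly proportional to an assumed dropout strength on which the SAP gives no figure. Score-related missingness is plausible, because 8.1.3 sets data after rescue from Day 29 to missing and 3.1.4 ties rescue to intolerable symptoms, but its strength is unknown.

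Third, the reach is small. Sections 4.2.6.3 and 4.2.7.3 make MI conditional on the amount of missing data, although 8.1.4 itself speaks of analyses that will be done. MI lies outside the hierarchy in 4.1.1, and 8.1.5 reads it for similar estimates rather than for significance. That stands and sets the grade.

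A reader might infer that the fill must bias the treatment effect. The documents do not support that: with dropout unrelated to scores there is no bias under either fill, only an SE that is too small.

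**Conclusion.** The concern holds as a minor point. The note, as written, states a deterministic fill that contradicts the regression-based MI and Rubin pooling of 8.1.2 and the sequential, trajectory-based MI of 8.1.4. The size depends on successive assumptions:

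- If the note is followed literally, the SE of the treatment difference is understated by about 5%, 9% and 14% at an assumed 10%, 20% and 30% missing.
- If dropout also depends on earlier scores, at an assumed log-odds of 0.5 to 1 per SD, the estimate is biased by about 0.03-0.18 SD against benralizumab (raw-score fill) or about 0.01-0.04 SD in its favour (mean-change fill).

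A reader might also infer that the trial's main conclusions or its type I error control are at risk. They are not. The primary and key secondary binary endpoints use non-responder imputation (3.1.5, Table 11), the continuous endpoints use a direct-likelihood MMRM (8.1.3), and the sample size does not depend on the note. Nor do the documents show that a constant fill is intended.

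**What to change.** Replace the note to Table 12 with:

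*Under both MAR and DRMI, missing values in the placebo arm are multiply imputed by random draws from the placebo-arm regression model of 8.1.2, conditional on the participant's own earlier scores and the covariates of the main model.*

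This uses the SAP's own procedure and adds no new method. It also removes the choice between raw scores and changes as the fill value.

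The cost is one reworded note and, if the code follows the literal wording, a change to the imputation program. In that case the SEs reported in these sensitivity analyses become slightly larger, because they now carry the uncertainty from missing placebo data. The primary analysis, the key secondary analyses, the MMRM and the sample size do not change.
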